6	3.4.1.1 Delayed/Late Listeria Infection	21-22	Safety Section revised to include clinical experience to-date with Lm clearance and the description of the index case of delayed/late listeria infection.	Per FDA Safety Section, revised to inform investigators/patients on the recent delayed/late listeria event.
7	5.2 Exclusion Criteria (#14)	28	New exclusion criterion was added to exclude subjects with implanted devices that pose high risks for colonization or inability of removal.	Exclusion criteria added to mitigate risk of colonization of foreign bodies and medical devices
8	5.2 Exclusion Criteria(#15)	28	New exclusion criterion was added to exclude subjects who are receiving or are expected to receive treatment with PI3K or TNFα inhibitors during study participation or in future.	Exclusion criteria added to mitigate risk of listeria infection.

#	Section	Page	Revision	Rationale
9	5.2 Exclusion Criteria #16	28	New exclusion criterion was added to exclude subjects with a known contraindication (e.g. allergies/sensitivities) to the administration of trimethoprim sulfamethoxazole and/or ampicillin.	Exclusion criterion added based on FDA recommendation of prophylaxis and 6-month antibiotic treatment.
10	5.2 Exclusion Criteria (#21)	29	New exclusion criterion added to exclude subjects who have undergone a major surgery or had a newly implanted artificial (prosthetic) joint(s), implants and/or devices where a minimum of 6 weeks has not elapsed from the time of surgery. Additional requirements for the resolution of all toxicities and/or complications was included.	Exclusion criteria added as a required safety update to mitigate potential listeria events.
11	6 Study Design and Treatment Plan	29	Updated antibiotic regimen added.	Inclusion added based on FDA recommendation of antibiotic regimen for prophylaxis during study treatment and 6 month course post-treatment.
12	7.3 Patient Study Participation	33	New section added to detail patient study participation duration.	Updated to include the 3 year Lm Surveillance Monitoring Phase
13	Table 5: Schedule of Events	34-35	Added Lm Surveillance Monitoring schedule which includes a 6 month post ADXS11-001 antibiotic (Trimethoprim/Sulfamethoxazole) treatment to mitigate the risk of delayed listeria infection. Text clarified in the table footnotes for consistency with the revised corresponding study procedure.	Safety updates and administrative clarifications per FDA recommendation.

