3.4.1.1 Delayed/Late Listeria Infection

ADXS11-001 has been attenuated over more in comparison to wild-type (wt)-*Lm*.

[figure not shown]
In a Phase 1 clinical study, in the absence of antibiotics, Lm was rapidly cleared from the blood. No Lm was detected in the blood of any subject beyond 48 hours post-dosing and no Lm was detected in the urine and feces in any subject at the highest dose of ADXS11-001 tested (1 x 10¹⁰ CFU) [11].

wt-*Lm* is known to form and persist within biofilms, especially on medical devices despite antibiotic treatment [12]. Although rare, medical device—related infections such as ventriculo-peritoneal shunt infection, peritoneovenous shunt infection, and prosthetic joint infection have been reported [13-16]. ADXS11-001is highly sensitive to antibiotics such as ampicillin and sulfamethoxazole/trimethoprim, which can be an effective treatment regimen for listeria infection. Therefore, subjects with implanted medical device(s) that pose a high risk for colonization and/or cannot be easily removed are excluded from this study. In addition, all subjects will receive a course of oral antibiotics

beginning on Day 4 (approximately 72 hours) after each dose of ADXS11-001 and for 6 months following the last dose of ADXS11-001 to aid in the eradication of the bacteria.

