8.5 Safety Follow-Up/Post-Treatment Visits

Safety follow-up will be conducted via a telephone call at 30 days (\pm 5 days) after the last ADXS11-001 infusion to confirm the resolution of any ongoing AEs and SAEs. Additional unscheduled visits may be considered as needed and at the discretion of the Investigator. Safety follow-up will also continue to be monitored for AEs and SAEs during the 3-year Lm surveillance period of the study (see below).

Surveillance monitoring for the detection of *Lm* will be initiated at the completion of study treatment according to the protocol or at the time of study discontinuation if earlier. This surveillance monitoring period will consist of a 6-month course of oral antibiotics,

obtaining a blood sample to monitor CBC, CMP, including CRP and ESR, and blood cultures at regular intervals. This testing will be performed on all subjects who have received at least 1 dose of ADXS11-001. It will occur every 3 months (±2 weeks) for 3 years beginning after the last dose of study treatment. If a persistent increase in CRP and/or ESR is observed with negative blood cultures for *Listeria* during this time, the subject should be evaluated and treated, as appropriate, for another possible cause. In the event that a definite cause has not been identified, subjects must continue to be monitored closely, including additional testing and a blood culture, for possible signs/symptoms of listeriosis. This testing may be performed at the investigational site or at another acceptable location following consultation with the Sponsor.

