11.5.2 Management and Surveillance of Listeria during Study Participation

In the event a subject experiences a persistent fever lasting 72 hours after receiving study treatment then the oral antibiotic regimen will be replaced by broad spectrum IV antibiotic treatment. If symptoms consistent with sepsis occur close to ADXS11-001 administration or at any time after ADXS11-001 administration, immediate medical attention must be sought. A microbial culture will be taken to identify the agent of sepsis and antibiotic sensitivity testing should be performed to confirm susceptibility. An infectious disease consult should be obtained for further management of these subjects.

All subjects will receive a 6-month course of an oral antibiotic regimen as a prophylactic measure following the completion of the last dose of ADXS11-001 treatment or at the time of study discontinuation. This additional safety measure is intended to eradicate *Lm* from the body.

Lm surveillance monitoring will also be initiated following the completion of the last dose of ADXS11-001 treatment or at the time of study discontinuation. This monitoring

will include obtaining a blood sample for CBC, comprehensive metabolic panel (CMP), including CRP and ESR, and blood cultures for the detection of *Listeria*. Testing will be performed on all subjects who have received at least 1 dose of ADXS11-001 and occur every 3 months (±2 weeks) for 3 years.

Should a diagnosis of listeriosis be made at any point after treatment with ADXS11-001 and the 6-month course of oral antibiotics are completed, immediate and intensive IV antibiotic treatment (ampicillin +/- gentamycin or other IV antibiotic regimen as indicated) is required. An infectious disease consult should be obtained. Based on each individual subject's case and at the discretion of the treating physician, the removal of any foreign medical object that has been present since treatment with ADXS11-001 was initiated may be warranted. It is extremely important that the Investigator, his/her research staff, other healthcare providers involved in the care of the subject as well as each subject participating in this study are educated and made aware of the signs and symptoms of listeriosis and the potential for delayed listeremia/listeriosis. Educational materials for the Investigator, research staff, health care providers and subjects will be prepared and educational training performed.

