11.6 ADXS11-001 Toxicities and Treatment

Please refer to Section 3.4.1 for summary information on the ADXS11-001 AE profile.

ADXS11-001 is a live attenuated bioengineered nonpathogenic strain of Lm, and one that is known to stimulate a strong innate immune response characterized by high levels of cytokine release from immune cells into the general circulation. This pattern of side effects is consistent with other immunotherapy agents.

The most likely AEs associated with ADXS11-001 are comprised primarily of individual flu-like symptoms (e.g., fever, chills, body ache, and fatigue) or cytokine release symptoms (e.g., headache, nausea, vomiting, tachycardia, shortness of breath, hypotension and rash). The symptoms usually present within 2-4 hours after the completion of infusions and are often mild to moderate and transient in nature or respond quickly to symptomatic treatment. In rare instances they may last up to 24 hours. No cumulative or delayed toxicity has been observed.

Less likely AE's include increase heart rate, low blood pressure, muscle aches, headaches, allergic reaction, changes in blood chemistry, changes in blood counts, and short term changes in liver function.

Rare but serious AEs include high fever and difficulty breathing and hypotension.

, ADXS11-001 has a tropism for the liver. Transient asymptomatic elevations of ALT and alkaline phosphatase were observed after dosing in the Phase 1 trial without prophylactic medication administration. For that reason, subjects with significant liver disease are excluded, and particular attention is to be paid to hepatic abnormalities.

Please reference the ADXS11-001 IB for complete information regarding AEs.

During the time the subjects are at the study site, the infusion line will be left in place to administer parenteral drugs, should that be necessary. As described in Section 11, subjects will be pretreated to minimize side effects of the study agent. The Investigator should observe the subjects for signs of inflammation and/or infection, including unremitting fever or vomiting, that require more intense therapy, and to treat them appropriately. All such treatments are to be listed on the eCRF.

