13.2 Collection of Safety Information

An AE is defined as any untoward medical occurrence in a subject or clinical investigation subject administered a pharmaceutical product and which does not necessarily have to have a causal relationship with this treatment. An AE can therefore be any unfavorable and unintended sign (including an abnormal laboratory finding, for example), symptom, or disease temporally associated with the use of a medicinal product or protocol-specified procedure, whether or not considered related to the medicinal product or protocol-specified procedure. Any worsening (i.e., any clinically significant adverse change in frequency and/or intensity) of a preexisting condition that is temporally associated with the use of the sponsor's product, is also an AE.

The Sponsor's product includes any pharmaceutical product, biological product, device, diagnostic agent or protocol-specified procedure, whether investigational (including placebo or active comparator medication) or marketed, manufactured by, licensed by, provided by or distributed by Advaxis for human use.

During clinical trials, AEs can be spontaneously reported or elicited during open-ended questioning, examination, or evaluation of a subject. In order to prevent reporting bias, subjects should not be questioned regarding the specific occurrence of 1 or more AEs.

AEs may occur during the course of the use of Advaxis' product in clinical trials or within the follow-up period specified by the protocol, or prescribed in clinical practice, from overdose (whether accidental or intentional), from abuse and from withdrawal.

AEs may also occur in screened subjects during any pre-allocation baseline period as a result of a protocol-specified intervention, including washout or discontinuation of usual therapy, diet, placebo treatment or a procedure.

All AEs will be recorded from the time the consent form is signed through 30 days following cessation of treatment during the study treatment period of the study. AEs and SAEs will be recorded during the 3-year *Lm* surveillance period of the study and at each examination on the AE eCRF. The reporting timeframe for AEs meeting any serious criteria is described in Section 13.7.1.

Disease progression associated with the underlying malignancy need not be reported as an "adverse event", per se. Naturally, it is captured as a part of the intended endpoints.

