		If yes, this is a positive dechallenge. If no, this is a negative dechallenge.
		(Note: This criterion is not applicable if: (1) the AE resulted in death or permanent disability; (2) the AE resolved/improved despite continuation of the Advaxis product; or (3) the trial is a single-dose drug trial); or (4) Advaxis product(s) is/are only used one time.)
	Rechallenge	Was the subject re-exposed to the Advaxis product in this study?
		If yes, did the AE recur or worsen?
		If yes, this is a positive rechallenge. If no, this is a negative rechallenge.
		(Note: This criterion is not applicable if: (1) the initial AE resulted in death or permanent disability, or (2) the trial is a single-dose drug trial); or (3) Advaxis product(s) is/are used only one time).
		NOTE: IF A RECHALLENGE IS PLANNED FOR AN ADVERSE EVENT WHICH WAS SERIOUS AND WHICH MAY HAVE BEEN CAUSED BY THE ADVAXIS PRODUCT, OR IF REEXPOSURE TO THE ADVAXIS PRODUCT POSES ADDITIONAL POTENTIAL SIGNIFICANT RISK TO THE SUBJECT, THEN THE RECHALLENGE MUST BE APPROVED IN ADVANCE BY THE U.S. CLINICAL MONITOR AS PER DOSE MODIFICATION GUIDELINES IN THE PROTOCOL.

	Consistency with Trial Treatment Profile	Is the clinical/pathological presentation of the AE consistent with previous knowledge regarding the Advaxis product or drug class pharmacology or toxicology?
		ll be reported on the case report forms /worksheets by an investigator who is a qualified physician according to his/her best clinical n of the above elements.
Record one of th	e following	Use the following scale of criteria as guidance (not all criteria must be present to be indicative of an Advaxis product relationship).
Definite:		The event follows a reasonable temporal sequence from administration of the study drug, the event follows a known response pattern to the study drug and based on the known pharmacology of the study drug, the event is clearly related to the effect of the study drug
Probable:		The event follows a reasonable temporal sequence from administration of the study drug and the event follows a known response pattern to the study drug AND the event cannot have been reasonably explained by an intercurrent medical condition or the event cannot be the effect of a concomitant medication

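### Section 11.6 says no delayed toxicity has been observed, at odds with the plan's own delayed-listeria sections; milder late cases can go unasked, be classed Unrelated on timing, and fall outside the AE summary

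*Combined protocol and SAP*

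**What the plan says.** - **Toxicity profile.** Section 11.6 first refers the reader to 3.4.1 for the AE profile. It then describes acute flu-like and cytokine release symptoms and ends that paragraph with "No cumulative or delayed toxicity has been observed".
- **Delayed infection.** Section 3.4.1 contains a subsection titled "Delayed/Late Listeria Infection". Section 11.5.2 says that investigators, research staff, other providers and subjects must know "the signs and symptoms of listeriosis and the potential for delayed listeremia/listeriosis", and plans training for it.
- **Surveillance.** Section 8.5, Section 11.5.2 and Table 5 (footnote 19) give every subject who received a dose a CBC, a CMP with CRP and ESR, and blood cultures every 3 months for 3 years. A 6-month oral antibiotic course runs at the start of that period. Section 8.5 also sets a telephone call 30 days after the last infusion.
- **How AEs are elicited.** Section 13.2 allows spontaneous reports, open-ended questions, examination and evaluation. To prevent reporting bias, it adds that "subjects should not be questioned regarding the specific occurrence of 1 or more AEs".
- **Causality.** The definitions of Unrelated in 13.2 and in Table 12 both list late timing as a ground. Table 12 also asks: "Is the clinical/pathological presentation of the AE consistent with previous knowledge regarding the Advaxis product".
- **Analysis.** Section 14.5.4 summarizes an AE if its onset is on treatment or within 30 days after the last dose, or if it began before Day 1 and worsened on therapy. The statistical sections name no analysis of the surveillance cultures, although the synopsis lists those cultures among the safety criteria.

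**The concern.** An investigator who turns to 11.6 for the toxicity profile reads an unqualified statement that nothing delayed has been seen. The same protocol runs a 3-year programme because something delayed may occur. The two messages meet when a subject reports a fever or a gastrointestinal illness many months after the last dose. Someone must then think to ask, decide whether it is related, and get it into the tables. At each of those steps the current text leans away from finding or counting a late, milder case.

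The treated population is small, so late events will be few and each one carries weight. The study assesses safety by comparing treatment-related AEs (Section 6), so attribution is not a side issue.

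**Working it through.** The plan states no figure on this point, so the check sets passages side by side, with simple arithmetic on the plan's own schedule.

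**1. Is 11.6 consistent with the rest?** Section 11.6 speaks of delayed toxicity in general and denies that any has been observed. The section it cites for the AE profile contains a subsection on delayed listeria infection. Section 11.5.2, shortly before it, treats awareness of delayed listeriosis as essential, and 8.5 builds surveillance around it. The summary of changes says that 3.4.1.1 was revised to include "the description of the index case of delayed/late listeria infection". That case description is not visible in the supplied 3.4.1.1, so the conflict rests on current Sections 3.4.1.1, 8.5 and 11.5.2, with the summary of changes only as support.

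**2. What does surveillance cover?**
- Scheduled draws: 36 months / 3 months = 12 per subject, at months 3, 6, ..., 36.
- Draws during or at the end of the 6-month antibiotic course: months 3 and 6, so 2 of 12. Section 3.4.1.1 describes the product as highly sensitive to these antibiotics.
- In Table 5 the Follow-Up column marks antibiotic dispensing, the telephone call, AE review and *Lm* surveillance. Physical examination, vital signs and ECOG status are not marked. Apart from the 30-day call, AE review is therefore the only scheduled look at symptoms.
- Section 8.5 calls for a watch on signs and symptoms of listeriosis, but only after a persistent CRP or ESR rise with negative cultures and no definite cause.
- Section 11.5.1 says a negative culture does not exclude infection when clinical suspicion is strong. Suspicion needs symptoms, and 13.2 says not to ask for specific ones.

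**3. Can a late case be classed Unrelated?** Yes, on timing alone, under 13.2 and again under Table 12. Neither makes an exception for listeriosis. The consistency item in Table 12 then points the investigator to prior knowledge of the product, which 11.6 partly supplies.

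**4. Would a late case be summarized?**
- Surveillance length: 3 x 365.25 = 1,096 days.
- Share after the 30-day onset window: 1 - 30/1,096 = 0.973, about 97%.
- A new listeriosis with onset in that 97% is recorded on the eCRF (13.2) but does not meet the onset rule in 14.5.4. That section also says generally that all AEs are summarized, and 14.1 promises listings, but the only stated timing rule leaves the case out.
- Laboratory data are summarized at each infusion, and surveillance draws come after the last infusion.

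**5. How few events?** The documents give no rate of delayed listeriosis, so the rates below are assumptions. With n = 15 at the RP2D (Section 14.3), the chance of at least one case is 1 - (1 - p)^15:
- p = 0.5%: 7%
- p = 1%: 14%
- p = 2%: 26%
- p = 5%: 54%

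If none is seen in 15, the one-sided 95% upper bound is 1 - 0.05^(1/15) = 18%. These figures show only that late cases will be rare and the estimate loose. They do not measure how likely a case is to be missed.

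**The case against.** The strongest reply is that detection does not depend on AE questioning, and for serious disease that stands. Cultures come with CRP and ESR at every draw. Section 11.5.2 requires immediate attention and a culture for sepsis symptoms at any time after dosing. Everyone concerned, including subjects, is to be taught the symptoms. Section 13.7.1 requires SAEs to be reported within 24 hours through the 3 years, related or not. Section 11.5.1 says that nearly all diagnosed listeriosis is invasive. A reader might infer that 13.2 leaves delayed listeriosis largely undetected; the documents do not support that.

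Four further objections have force:
- **Observed versus potential.** Section 11.6 reports what has been observed, while 11.5.2 warns of what may happen, and the sentence closes a paragraph on acute symptoms. The visible text therefore does not prove the sentence false. It is still unqualified, and it still clashes with the sections around it.
- **Wording of 13.2.** It says should not, gives an anti-bias reason, and permits examination and evaluation. It is not an absolute ban. The 30-day call in 8.5 exists "to confirm the resolution of any ongoing AEs and SAEs". Asking about an AE already reported is follow-up, so it does not breach 13.2.
- **Attribution and the observed rate.** A reader might infer that classing a case as Unrelated turns one observed case into none. It does not: 14.5.4 summarizes incidence overall and tabulates causality as a separate attribute. It is the 30-day onset rule that takes a late case out of the AE summary.
- **Table 12.** Its consistency item is one of several and also refers to the drug class. A *Listeria* isolate after a live *Listeria* product would fit it. The late-timing criterion is the firmer ground for concern.

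It can also be said that fever, muscle ache and gastrointestinal upset are non-specific in advanced cervical cancer. That is a real cost of asking, and a reason to keep solicited reports apart.

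**Conclusion.** The point holds in a limited form and should be corrected.

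- The 11.6 sentence is inconsistent with 3.4.1.1, 8.5 and 11.5.2, and the passages must be reconciled. Whether an observed case makes it factually wrong cannot be settled from the supplied text.
- The ascertainment gap is confined to non-serious, transient or culture-negative illness between the 12 quarterly draws. Its size cannot be estimated, because the documents give neither a rate of delayed listeriosis nor the sensitivity of open questioning.
- The attribution and reporting gaps are textual and firmer: late timing is by itself a ground for Unrelated, and about 97% of the surveillance period lies beyond the 30-day onset rule.

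The 97% assumes that surveillance runs the full 3 years from the last dose. The figures for rarity assume 15 subjects at the RP2D, and that expansion is optional. The escalation part alone enrolls 6 to 12 in total.

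**What to change.** 1. **Section 11.6.** Reword the sentence to agree with 3.4.1.1 and 11.5.2. If it was meant only for the acute symptoms it follows, say so and refer the reader to those sections for delayed listeria infection.
2. **Section 13.2.** Keep the open question first. Add an exception: at the 30-day call and at each surveillance contact, then ask a fixed short list of the listeriosis symptoms already given in 11.5.1. Flag these answers as solicited and tabulate them apart from spontaneously reported AEs.
3. **Section 13.2 and Table 12.** State that late onset alone does not make a listeriosis event Unrelated.
4. **Section 14.5.4.** Add a table or listing of AEs with onset during surveillance, and of surveillance culture results, by dose.

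The cost is a few wording changes, a one-page checklist at contacts already scheduled, and one or two added outputs. The downside is more non-specific reports of fever, muscle ache and gastrointestinal symptoms. The separate solicited table contains that and keeps the anti-bias purpose of 13.2. No dose, schedule or treatment rule changes.
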